# **RESEARCH REFERENCE NUMBERS**

IRAS Number: 326517

SPONSORS Number: ETH2425-0099

FUNDERS Number: NIHR204418

TRIAL REGISTRY NUMBER AND DATE: To be applied.

# PROTOCOL VERSION NUMBER AND DATE

Version 2.0 dated 01.05.2025

# **Version Control**

Version	Date	Author	Reason
V0.1	12th March 2024	[name]	First Draft (Feasibility Study only)
V0.5	22 nd August 2024	[name], [name], [name], et al.	Near final
V1.0	3 rd September 2024	PEGASUS PMG	Final
V1.1	15 th October 2024	PEGASUS PMG	Amended following REC comments
V1.2	4 th February 2025	PEGASUS PMG	Amended with changes in PI in site, timeline and measures used
V2.0	1 st May 2025	PEGASUS PMG	Amended with changes in outcome measures and extended duration
V2.1	5 th of August 2025	[name]	Amended with changes in team staff, minor documentation clarification and welcome letter
V2.2	29 th September 2025	[name], [name]	Amended with minor documentation clarification
V2.3	21 st November 2025	PEGASUS PMG	Minor documentation changes

### **ii. LIST OF ABBREVIATIONS**

Define all unusual or 'technical' terms related to the trial. Add or delete as appropriate to your trial. Maintain alphabetical order for ease of reference.

AE Adverse Event
AR Adverse Reaction
CA Competent Authority
CI Chief Investigator
CRF Case Report Form

CRO Contract Research Organisation

CTU Clinical Trials Unit

CVD Cardiovascular Disease

DMC Data Monitoring Committee

GCP Good Clinical Practice

HDL High density lipid

ICC Intracluster correlation coefficient

ICF Informed Consent Form

ICH International Conference on Harmonisation of technical requirements for

registration of pharmaceuticals for human use.

ISRCTN International Standard Randomised Controlled Trials Number

NHS R&D National Health Service Research & Development

LER Lived Experience Researcher

LDL Low density lipid

NIMP Non-Investigational Medicinal Product

PI Principal Investigator

PIC Participant Identification Centre
PIS Participant Information Sheet
PMG Programme Management Group
PSC Programme Steering Committee
PW/PSW Peer Worker/ Peer Support Worker

QA Quality Assurance
QC Quality Control
QP Qualified Person

RCT Randomised Control Trial
REC Research Ethics Committee

SAE Serious Adverse Event

SAR Serious Adverse Reaction
SDV Source Data Verification
SMI Severe Mental Illness

SOP Standard Operating Procedure

SSI Site Specific Information

SUSAR Suspected Unexpected Serious Adverse Reaction

T2D Type 2 Diabetes

# iii. TRIAL SUMMARY

Trial Title	A peer supported/led group programme for people with severe mental illness to reduce risk of cardiovascular disease (PEGASUS): A feasibility evaluation study					
Internal ref. no. (or short title)	PEGASUS feasibility study wit metabolic syndrome	h people with SMI and				
Clinical Phase	Feasibility testing					
Trial Design	Non-randomised mixed metho	d feasibility study				
Trial Participants	People with Severe Mental Illn syndrome	ess (SMI) and metabolic				
Planned Sample Size	40 service user participants; and up to 16 intervention staff (2 peer workers and 2 mental health nurses (or other mental health professionals or non- registered practitioners with appropriate training per site) for post-intervention focus group study					
Treatment duration	6 months					
Follow up duration	3 and 6 months post baseline					
Planned Trial Period	9 months					
	Objectives	Outcome Measures				
Primary	Research aims: To assess the feasibility of the peer- supported group clinic intervention	Section 3.6				
	To assess recruitment and retention rates over the study period.					

### iv. FUNDING AND SUPPORT IN KIND

FUNDER(S)  (Names and contact details of ALL organisations providing funding and/or support in kind for this trial)	FINANCIAL AND NON FINANCIALSUPPORT GIVEN
NIHR Programme Grant for Applied Research https://www.nihr.ac.uk/explore-nihr/funding-programmes/programme-grants-for-applied-research.htm	Research costs £2,679,253.97

### v. ROLE OF TRIAL SPONSOR AND FUNDER

The sponsor (City St George's, University of London) holds overall responsibility for the initiation and management of the study.

The funder (NIHR) plays no role in study design, conduct, data analysis and interpretation, manuscript writing, or dissemination of results. Nor does the funder control the final decision regarding any of these aspects of the study.

# vi. ROLES AND RESPONSIBILITIES OF TRIAL MANAGEMENT COMMITEES/GROUPS & INDIVIDUALS

**Programme Steering Committee:** 

The research described in this protocol forms part of a larger research programme. An independent programme steering committee (PSC) will meet at least biannually to provide independent oversight, advice and guidance to the programme. The PSC comprises 11 independent members (see PSC membership), including a chair, an independent statistician, at least one other academic or clinical member with appropriate expertise and two PPI members. For the current feasibility study, the PSC has agreed to take on the role of an independent Data Management Committee (DMC).

The PSC will be attended by [name] and/or [name] and/or [name] as co-Cls plus other members of the programme team as necessary. The programme team will report to the PSC on progress in delivering the programme as funded. Minutes will be signed off by the PSC chair and submitted to NIHR. The programme team will seek the advice of the PSC on any major amendments to ethical approval.

### Lived Experience Advisory Group:

An independent Lived Experience Advisory Group (LEAG) will meet approximately three times per year (15 meetings over 5 years of the entire programme) and will advise the study team on important aspects of undertaking the research, including (but not limited to) development of data collection materials, co-production of the peer-supported group intervention, participant recruitment strategies, interpretation of data, and writing up and dissemination of research outputs.

# vii. Protocol contributors

The protocol has been designed by the study team, as named above and was informed by members of the LEAG.

viii. KEY WORDS:

Behaviour change; cardiometabolic risk; co-production; feasibility study; group clinic; peer support; severe mental illness

# ix. TRIAL FLOW CHART

A Gantt chart for the current feasibility study (updated for v.2.0):

	2024			2025										2026					
	Sep	Oct	Nov	Dec	Jan	Feb	Mar	Apr	May	Jun	Jul	Aug	Sep	Oct	Nov	Dec	Jan	Feb	Mar
Project Month	0	1	2	3	4	5	6	7	8	9	10	11	12	13	14	15	16	17	18
PEGASUS Programme Management Group	Х	Х	Х	Х	Χ	Х	Х	Х	Х	Х	Х	Х	Х	Х	Х	Х	Х	Х	Х
Programme Steering Committee (and DMC for feasibility study)		Х						х			Х							Х	
Lived Experience Advisory Group (LEAG)	Х			Х							Х				Х				Х
HRA ethics and site C&C	Х	Х				Х			Х										
Co-design workshops	Х		Х	Х							Х						Х		
SOP/CRF and CSO & researcher training						Х	Х	Х	Х	Х	Х								
Manual development					Χ	Х	Х	Х	Х										
Intervention staff training and supervision									Х	Х	Х	Х	Х	Х	Х	Х	Х		
Staff recruitment							Х	Х	Х	Х	Х	Х							
Service user (SU) participant recruitment									Х	Х	Х	Х	Х						
Eligibility screening									Х	Х	Х	Х	Х						
Intervention delivery										Х	Х	Х	Х	Х	Х	Х	Х		
Data collection									Х	Х	Х	Х	Х	Х	Х	Х	Х		
Interviews/focus group with SU participants and staff												Х	X			Х	X		
Data analysis											Х	Х	Х	Х	Х	Х	Х		
Refining intervention and RCT design													Х	Х	Х	Х	Х	Х	Х

See also Figure 1 – Participant flow diagram in Section 7.1.2

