# 3.6 Table of endpoints/outcomes

Objectives	Outcome Measures	Timepoint(s) of evaluation of this outcome measure (if applicable)
Primary Objectives	
 
Participant recruitment & retention rate
 
Acceptability (as assessed by focus group/interview
 
Feasibility of collecting:
 
Waist and hip circumference
 
BMI
 
Triglycerides
 
HDL-cholesterol
 
LDL-cholesterol
 
Total cholesterol
 
HbA1c
 
Blood pressure
 
Questionnaires as listed in Section 7.7 (so to determine mean and standard deviation (SD) of measurements required for the future full RCT)
 
	Baseline (pre-intervention), 3 month and 6-month follow up

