### 10.8 Procedure(s) to account for missing or spurious data

All individuals who are included within the study will be followed up at six months unless the participant has withdrawn from the study. Missing data will be described using descriptive statistics. The proportion of missing data will be collated per measure to assess item completeness.

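### The v2.0 timetable ends data collection in January 2026, before the 6-month visits of participants with August or September 2025 baselines fall due, and the stated 9-month trial period is too short

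*Protocol*

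**What the plan says.** Section ix (Trial flow chart) opens with "A Gantt chart for the current feasibility study (updated for v.2.0" and sets out 19 monthly columns, from September 2024 (project month 0) to March 2026 (month 18). The row "Service user (SU) participant recruitment" is marked in months 8 to 12 (May to September 2025), and eligibility screening has the same marks. The row "Data collection" is marked in months 8 to 16 (May 2025 to January 2026) and is blank in February and March 2026. "Intervention delivery" runs from month 9 to month 16. Data analysis and the last interviews and focus groups also end in month 16.

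Section iii (Trial summary) gives follow-up as "3 and 6 months post baseline" and, under "Planned Trial Period", 9 months. Section 3.6 lists the outcome timepoints as "Baseline (pre-intervention), 3 month and 6-month follow up". Section 10.8 states: "All individuals who are included within the study will be followed up at six months unless the participant has withdrawn from the study". Section 10.3.2 makes retention and completeness of data the primary outcome analysis, and Section 10.1 bases the sample size on the precision of the retention rate.

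**The concern.** The follow-up clock starts at each participant's own baseline, so the last 6-month visit falls six months after the last baseline. The chart leaves only four months between the end of recruitment and the end of data collection. The recruitment window, the data collection window, the 9-month period and the six-month follow-up of everyone cannot all hold.

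If sites and staff contracts were planned from the chart, late recruits would lack 6-month data for calendar reasons. That would affect 6-month retention, data completeness, and the end-of-intervention estimate of metabolic syndrome reversal, which Sections 3.1 and 10.3 want for the design of the main trial. Section 10.1 assumes four groups of 10 at four sites, so a site that filled late could be short of 6-month data for its whole group. The site-level retention figures planned in Section 10.4 would suffer most.

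**Working it through.** **The plan's own figure.** Data collection in months 8 to 16 is 16 − 8 + 1 = 9 months, which matches the 9-month trial period in the summary. The period therefore appears to have been read off the data collection row.

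**Due dates.** 6-month visit month = baseline month + 6; the last charted data collection month is 16.

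| Baseline | 3-month visit | 6-month visit | 6-month visit within chart? |
|---|---|---|---|
| May 2025 (8) | Aug 2025 | Nov 2025 (14) | yes |
| Jun 2025 (9) | Sep 2025 | Dec 2025 (15) | yes |
| Jul 2025 (10) | Oct 2025 | Jan 2026 (16) | yes, last month |
| Aug 2025 (11) | Nov 2025 | Feb 2026 (17) | no |
| Sep 2025 (12) | Dec 2025 | Mar 2026 (18) | no |

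Two of the five recruitment months fail at six months; none fails at three. The last baseline that fits is 31 July 2025. First recruitment to last 6-month visit is months 8 to 18, that is 18 − 8 + 1 = 11 months.

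**Share affected.** The documents give no accrual pattern, so these are assumptions.

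- Even accrual, baseline on the day of recruitment: 1 May to 30 September is 153 days, and 1 May to 31 July is 31 + 30 + 31 = 92 days. Affected: (153 − 92)/153 = 61/153 = 40%, about 16 of 40.
- Even accrual, baseline 14 days after screening (the full window in Section 7.6): the last screening date that fits is 17 July, or 78 days. Affected: 75/153 = 49%, about 20 of 40.
- Whole groups of 10: with no group, one, two or three groups having their baselines in August or September, 0%, 25%, 50% or 75% are affected. Delivery starts in June, so at least one group is presumably early.

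**Precision if the affected participants have no 6-month data.** Inputs from Section 10.1: four groups of 10, ICC 0.03, retention 85%. Half-width = 1.96 × √[p(1 − p) × DE / n], with DE = 1 + (m − 1) × ICC.

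- n = 40, m = 10: DE = 1 + 9 × 0.03 = 1.27; effective n = 40/1.27 = 31.5; half-width = 1.96 × √(0.1275/31.5) = 12.5%.
- n = 24, taken as four groups of 6: DE = 1 + 5 × 0.03 = 1.15; effective n = 24/1.15 = 20.9; half-width = 1.96 × √(0.1275/20.9) = 15.3%.

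Section 10.1 states 14%. An exact (Clopper-Pearson) interval on an effective n of 31.5 gives 13.7%, so the stated margin is attainable by a standard method and is not in question here. The like-for-like comparison is 12.5% with 15.3%.

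**The case against.** The strongest reply is that a Gantt chart is a planning aid and not a rule for closing follow-up. Section 7.12 ends the study when data collection and analysis are complete, Section 10.8 requires six-month follow-up of everyone still in, and nothing tells sites to stop visits in January. On the operative text late recruits would still be seen, and it is the chart that is wrong. This stands as far as it goes: a reader might infer that late recruits cannot have a 6-month visit, and the documents do not say that. But the reply does not reconcile the chart or the 9 months with the follow-up rule.

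Other stronger readings also lack support:

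- That a true 85% retention would be reported as about 51% (0.85 × 24/40). This needs visits not yet due to be counted as losses. Section 7.7 records reasons for dropout and Section 10.3.1 plans a flow diagram, so the two can be told apart.
- That 60% of participants are affected, from the one-month enrolment-to-baseline spacing in Appendix A. Section 7.6 puts baseline within two weeks of screening, so under even accrual about 50% is the ceiling.
- That a group starting in October is in conflict with the plan because 12 fortnightly clinics do not fit by January. Section 7.1 allows four to six months, and Section 8.1 leaves the final number, duration and frequency of sessions open.
- That retention is defined only at six months. Section 3.6 lists three timepoints and Section 10.3.2 names none. Six months is one of those listed, and the one that Section 10.8 requires for everyone.

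**Conclusion.** The timetable contradicts the follow-up rule. Charted data collection ends up to two months before the last 6-month visits of participants with baselines in the planned recruitment window, and the 9-month period is at least two months short of the 11 needed. This follows from the protocol's own dates and needs no assumption beyond a baseline in the month of recruitment.

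How many participants are affected is uncertain. It is about 40% to 50% under even accrual, which is an assumption, and anywhere from none to well above that with group-wise recruitment. The widening of the half-width from 12.5% to 15.3% applies only if the chart is followed, 24 participants are evaluable and they are spread evenly over the four groups. That is a modest loss of precision. The larger risk is that 6-month data are missing for whole late-filling groups for reasons unrelated to the intervention. The error lies in the timetable; the endpoints and analysis methods are not at fault.

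**What to change.** Extend the data collection row to at least March 2026, with the end of data analysis and of the post-intervention interviews moved where needed, and restate the planned trial period as at least 11 months. Say whether baselines must be complete by 30 September. If a participant screened that day uses the full two weeks, baseline falls on 14 October and the 6-month visit on 14 April 2026, just past the chart's last column.

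If the January 2026 end is fixed, end baseline assessments by 31 July 2025 and shorten the recruitment and screening rows to match. The version control table carries entries up to 21 November 2025, so if that date has already passed only the first route remains.

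Under either route, keep all included participants in the analysis, as Section 10.7 requires. Limiting the retention denominator to those whose visit fell due in time would cut against that section. Report any 6-month visit not reached because of calendar closure separately from dropout in the flow diagram.

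The cost is a timeline amendment and up to two more months of field time (about two weeks more in the mid-October case). The chart already runs to March 2026, and no visit is added beyond those the protocol already requires.

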### STUDY PROTOCOL

A peer supported/led group programme for people with severe mental illness to reduce risk of cardiovascular disease: A feasibility evaluation study

(Short title: PEGASUS feasibility study with people with SMI and metabolic syndrome)

### **BACKGROUND**

People with a diagnosis of severe mental illness (SMI) such as schizophrenia, bipolar disorder and other psychoses, have poorer physical health and die on average 15-20 years younger than people without SMI. People with SMI have approximately 50% increased risk of developing cardiometabolic disease (CVD), the single biggest contributor to premature death, and a two to threefold risk of developing type 2 diabetes mellitus (T2D) compared to people without SMI. There is a 'double disadvantage' for people from racialised communities who can have an elevated risk of poor metabolic health, compounded by higher rates of diagnosis of SMI. People diagnosed with SMI should be offered routine monitoring of weight, and cardiometabolic and metabolic indicators of morbidity and these indicators should be audited in the annual team report. Trusts should ensure compliance with quality standards on the monitoring and treatment of cardiometabolic and metabolic disease in people with psychosis or schizophrenia through board-level performance indicators

There is systematic under-recognition and under-treatment of CVD and its risk factors in people with SMI in primary care, resulting in one of the greatest multi-morbidity and health inequality gaps in England. People with SMI are three times more likely to attend A&E with an urgent physical health need and almost five times more likely to be admitted as an emergency case compared to people without SMI.

In England, SMI has been estimated to cost £7.9 billion, 30% of this direct treatment costs and 70% indirect costs to individuals, informal carers and society in terms of lost productivity and premature mortality. A large proportion of treatment costs is for physical healthcare. For example, in a study of people on the Clinical Practice Research Datalink database, annual healthcare costs in England for T2D and SMI averaged £4059, of which £2745 was for non-mental health related hospital inpatient stays. Costs for those with T2D and SMI were higher than for people with T2D alone by £1930, of which £1207 related to non-mental health related hospital inpatient stays. Comorbid hypertension was one of the key predictors of higher costs among people with T2D and SMI.

The range of challenges to improving physical health for people with SMI include antipsychotic induced side-effects including weight gain and sedation, social isolation, low motivation and self-efficacy related to negative symptoms, social stigma, lack of support for behavioural change and difficulties in accessing disjointed physical and mental health care. Key determinants of self-management of physical health among people with SMI include factors that affect people's motivation to look after their physical health, such as emotional wellbeing, burden of living with SMI, beliefs about ability to self-manage, and having the skills to establish and maintain routines . Social isolation, widespread among people with SMI, is a barrier to physical health self-management  while social support facilitates self-management through encouragement, practical support and shared experiences. Residency in areas of higher own-group density for people from racialised communities might buffer against social isolation and be associated with exposure to

stronger health-protective social norms, which may ultimately protect against premature mortality in severe mental illness.

Lack of integration between physical and mental health services, including perceived jurisdictional boundaries between sectors, contributes to low confidence among mental health professionals in their skills to manage physical health, and among physical health professionals in their communication skills with patients with SMI. Across healthcare sectors, it is also well established that stigma and diagnostic overshadowing - i.e. misattribution of physical symptoms to mental illness - contribute to under-recognition and treatment of physical health conditions in people with a SMI. Improving the physical health of people with SMI is a healthcare priority. Better integration of physical and mental health services is widely recommended, however, optimal models have not yet been found.

This research offers a comprehensive intervention to CVD risk reduction specifically targeting people with SMI, using peer-led multi-goals approaches which have proven benefits(37). Our study has also paid particular attention to the intersecting disadvantages in access, experiences and outcomes faced by people from minority ethnic communities. Therefore, where possible we will attempt to recruit at least one peer worker and/ or nurse to the intervention team at each site who share similar heritage and culture to racialised communities who make up a substantial proportion of the population locally (e.g. the Bengali/ Bangladeshi community in Tower Hamlets in East London).

### 2 RATIONALE

There is a strong rationale for developing and evaluating an intervention, specifically addressing challenges for people with SMI, aimed at reducing risks and subsequent costs of CVD. Recent UK trials for physical health of people with SMI have not achieved improvements in primary outcomes including total cholesterol,weight or health-related quality of life. These interventions used established behavioural change techniques, such as goal-setting and action planning, but failed to achieve lifestyle change necessary to reduce CVD risk. Other recent studies largely address single risk factors for cardiometabolic health and evaluate single goal interventions (while for the most part not specifically addressing issues of social isolation and poor social support that compound physical and mental health challenges for people with SMI). There is good evidence indicating that multiple goal interventions, and the achievement of multiple goals, is associated with overall impact on cardiometabolic health but what is most important is the quality of the intervention.

There remains a need for a study that addresses the full range of challenges faced by people with SMI in reducing CVD risk. We are using participatory action research approach to co-produce a culturally responsive lifestyle intervention that combines: a) a self-management programme targeted to address the range of specific challenges faced by people with SMI to looking after their physical health; b) peer support to improve social inclusion and self-efficacy; c) a group clinic model to ensure integration of physical and mental health services. The research described in this protocol will assess the feasibility of the intervention.

# 2.1 Assessment and management of risk

This feasibility study is categorised as Type A = No higher risk than usual care.

There are few anticipated adverse effects of this structured lifestyle intervention. The development of the intervention ensured that it was tailored to the needs of people with SMI. There is a risk that anxiety about weight and its complications may be increased. If the intervention is unsuccessful this may lead to feelings of poor self-esteem. These risks probably are outweighed by the risk of widening health inequality and worsening health among people with SMI if the intervention is not assessed.

Blood sample collection for anthropometric data analysis is already part of routine physical health checks (at least annually for individuals on the GP Severe Mental Illness List). The risks such as increased anxiety and discomfort over short duration of time incurred is no higher than usual care.

